### 4.0 Study Intervention

4.1 Description: This nutritional intervention is designed to accelerate the addition of macronutrients over the first week of life to minimize the period of malnutrition, and is based upon the findings of numerous smaller, less comprehensive studies and expert opinion. Once consent is obtained, and the infant is admitted to the NICU, enrolled infants will be randomized to either receive parenteral nutrition per the standard NICU parenteral nutrition protocol or via the enhanced nutrition protocol for the first week of life via random envelope selection. Stratified

block randomization will be performed. Infants will be stratified by gestational age (22-25, 26-29, 30-32 weeks). Within each stratum, permuted block randomization will ensure that study personal are unable to predict treatment allocation. Infants

randomized to the enhanced nutrition protocol will receive starter total parenteral nutrition (TPN) initiated at 80 mls/kg/day to provide protein at 4 grams/kg/day and a glucose infusion rate (GIR) of ~5.5 mgs/kg/min as soon as IV access has been obtained. Enhanced nutrition protocol infants will also be started on intralipids (IL) at 2 grams/kg/day once IV access is obtained. Infants randomized to the enhanced nutrition protocol will receive 4 grams/kg/day of protein throughout the first week of life. IL will be increased to 3 grams/kg/day on day of life (DOL) 2 and to 3.5 grams/kg/day on DOL 3. They will remain on this amount for at least the first week of life or until sufficient enteral feeding volumes have been established. GIR will be advanced by  $\sim 1.5 \text{ mgs/kg/min per day}$ throughout the first week of life to a maximum of 12-14 mgs/kg/min. Again, they will then remain on this amount until sufficient enteral feedings have been established (typically approximately 1-2 weeks). Infants randomized to the standard nutrition protocol will receive macronutrients per the caregivers discretion, most commonly initiated with starter TPN at 60 mls/kg/day giving 3 grams/kg/day of protein and a GIR of ~4 and IL provided at 0-1 gram/kg/day. Advancement is most typically by 1

mg/kg/min per day for GIR and 1 gram/kg/day per day for IL and protein in the standard NICU protocol. Pertinent aspects of the differences in nutritional treatment in intervention and control groups are summarized in the table below

	Day 1	Day 2	Day 3	Day 4	Day 5	Day 6	Day 7	
Control								
GIR	4.2	5	6	7	8	9	10	

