### 5.0 **Procedures Involved**

5.1 Study Design: This exploratory study will use a simple randomized controlled trial design, and the parents, investigators, and all study

personnel (other than the in-patient study coordinator who oversees the ordering of the parenteral nutrition, the dietician and the data analyst in charge of assessing results of the study) will be blinded as to group assignment.

5.2 Study Procedures: Study Sample: Inclusions: We will include VLBW (birth weight <1500grams) preterm (gestational age (GA) at birth < 32 weeks) infants admitted to the University of Minnesota Masonic Children's Hospital NICU, for which written informed consent can be secured from a parent within 12 hours of birth. Exclusions: Infants who are diagnosed prenatally with a clinical condition (other than prematurity) that is known to affect growth rate, adiposity, or neurocognitive development, who experienced severe birth asphyxia, who are enrolled in another study affecting nutritional management, or who are likely to be transferred out of the NICU will be excluded from participation. We will attempt to enroll an equal number of female and male subjects, as well as those from a variety of racial and ethnic backgrounds.

Admissions to the antepartum unit and to the NICU will be screened daily by the inpatient research coordinator for potential eligibility for the trial. Once identified, the coordinator will present the mother/parents with a study brochure and offer to share more information and answer questions regarding the study if the family is interested. When possible, consent will be obtained prior to delivery. If unable to obtain consent prior to the infants delivery, the family will be approached within 12 hours of delivery to explain the study, answer questions and obtain consent. They will be allowed ample time to consider participation, as well as to ask questions of the clinical care team/ PI regarding the study.

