Markers of Growth hormone axis activity (Outcomes for Aim 3): IGF-1 and IGFBP3 levels will be obtained in serum at 1 week of age and ~35 weeks CA. These specific markers were chosen as associations have been seen between linear growth, FFM gains, metabolic risk (e.g. increased adiposity and higher blood pressure), neurodevelopmental outcomes and IGF-1 and IGFBP3 in preterm born infants . IGF-1 and IGFBP3 will be analyzed by the Fairview Clinical Laboratory.

Additional Measures: The randomized design of this trial is expected to make the distribution of potential confounder values and characteristics similar in the intervention and control groups. Nonetheless, to confirm their equivalence and to describe the study sample, we will obtain birth anthropometrics, maternal age, education, and ethnicity, infant sex, gestational age at birth, weight-for-age z score at birth, and degree of illness from the medical record or parental self-report at enrollment. Degree of illness will be assessed using the Score for Neonatal Acute Physiology (SNAP) on DOL#1, 7, 14 and  $21^{34-35}$ . We will also collect data on other non-specific markers of illness, including days on the ventilator, requirement for blood pressure support, sepsis evaluations and antibiotic therapy, steroid administration, necrotizing enterocolitis (NEC), diagnosis of chronic lung disease and retinopathy of prematurity (ROP) etc. These measures will also allow us to track the safety of the intervention to ensure that rates of these common morbidities are similar in both groups.

5.3 Storage and Access: The records of this study will be kept private. In any publications or presentations, we will not include any information that will make it possible to identify the mother or baby as a subject. Any hard copies of the baby's research records will be kept in a locked desk in the locked office of the PI, co-I or study coordinator, and will be identified ONLY by an assigned study ID number (other identifying information will be removed). The study information will not be recorded in the medical record. These de-identified data will be entered into electronic format for storage and analysis; only the PI, co-Is, study coordinators and data analyst will have access to this electronic dataset.

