#### **12.0 Local Recruitment Methods**

12.1 Recruitment Process: Admissions to the antepartum unit and to the NICU will be screened daily by the inpatient research coordinator for potential eligibility for the trial. Once identified, the coordinator will present the mother/parents with a study brochure and offer to share more information and answer questions regarding the study if the family is interested. When possible, and if there is IRB approval for this, consent will be obtained prior to delivery. If unable to obtain consent prior to the infant's delivery, the family will be approached within 12 hours of delivery to explain the study, answer questions and obtain consent. They will be allowed ample time to consider participation, as well as to ask questions of the clinical care team/PI regarding the study.

- 12.2 Source of Participants: The Epic (EMR) census for antepartum, labor and delivery and the NICU will be screened by the research coordinator.
- 12.3 Identification of Potential Participants: The unit census will be reviewed daily by the inpatient research coordinator to identify eligible patients. These patients will be drawn from the PI's patient population. Prior to birth, this will include mothers who have had a Neonatal Intensive Care Unit consult placed. After birth, parents whose infant is under the care of the PI and/or her colleagues will be approached. Patients will not selfidentify, but rather will be approached based on eligibility criteria that is contained in the medical record (i.e. gestational age). The inpatient study coordinator will present the parent(s) with a brochure describing the study. Following this initial contact, the study coordinator will follow-up with parents at their convenience to describe the study in more detail and answer any questions before obtaining consent. The family will also have an opportunity to meet with the PI or another neonatologist if requested to answer questions regarding the study. Those patients who have "research opt out" in their medical record will not be approached for participation in this study.
- 12.4 Recruitment Materials: Parents will initially be given a study brochure that generally describes the study. If the parents are then interested in hearing more about the study, they will be given a consent form and a time to discuss the details of the study with the inpatient study coordinator, their care teams and/or the PI.

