#### 16.0 Data Management

15.1 Data Analysis Plan: Data from the various domains will be entered by the study personnel into a web-based secure database (RedCap) for storage, retrieval and analysis. The NICU dietician is responsible for abstracting nutritional data from the electronic medical record (Epic). ADP data will be entered into the database by the study coordinators. ERP data will be abstracted by [name] and cleaned of artifacts as previously described. The data analyst will examine each variable for outliers and distributional properties and flag and correct entry errors where possible

and will log-transform or otherwise normalize variables prior to analysis. From RedCap all datasets will then be securely stored using Box.com per the HRPP policy. They may need to be downloaded to University/AHC desktops for statistical analysis, however only a subset of the team will be given access to all files (study coordinator and PI) and the rest will have access to the de-identified files only. These laptops are password protected and maintained by the AHC. Although we do not anticipate many missing values in this short-term follow-up study, multiple imputation methods (e.g., Proc MI in SAS) will be used if missing data can reasonably be considered missing at random. Analyses will also be run without imputation and results compared. Analyses will be carried out using SAS version 9.4 (SAS Institute Inc.) using an intent-to-treat approach, with a 2tailed p<0.05 as the threshold for statistical significance. For Specific Aims 1, 2, and 3, body composition data, neurodevelopmental outcomes, and IGF-1 and IGFBP3 will be treated as continuously-distributed variables assessed at multiple time points. For the ERP outcomes (which are measured twice), the primary hypotheses will be addressed using a simple general linear regression model for term-equivalent measures, and another similar model for 4 month corrected age measures, with assigned group as the independent variable in both cases. For FFM (with up to 10 repeated measures) and IGF-1 models, mixed effects regression models (using

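### Permuted blocks do not make allocation unpredictable to staff who know past assignments, and the data analyst is unblinded while correction and transformation choices are still open

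*Combined protocol and SAP*

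**What the plan says.** **Who is unblinded.** Section 5.1 blinds parents, investigators and study personnel, with three exceptions: "the in-patient study coordinator who oversees the ordering of the parenteral nutrition, the dietician and the data analyst in charge of assessing results". The exemption has no end point, such as a data lock, and no section says when the analyst first sees arm labels.

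**What the analyst decides.** Section 16.0 (the subsection numbered 15.1) states: "The data analyst will examine each variable for outliers and distributional properties and flag and correct entry errors where possible". The same sentence goes on to log transformation or some other normalisation before analysis. It gives no list of variables and no rule for choosing. Multiple imputation depends on a judgement that data are missing at random.

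**How infants are allocated.** Section 4.1 describes permuted blocks within three gestational-age strata and claims that "permuted block randomization will ensure that study personal are unable to predict treatment allocation". Allocation is "via random envelope selection". No block length, envelope specification or custodian is given. The order of events is stated: "Once consent is obtained, and the infant is admitted to the NICU, enrolled infants will be randomized".

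**Who recruits.** Section 12.3 says: "The inpatient study coordinator will present the parent(s) with a brochure describing the study". This is the title that Section 5.1 leaves unblinded. Elsewhere the role is plural: Section 5.3 says "only the PI, co-Is, study coordinators and data analyst will have access to this electronic dataset", and Section 16.0 says "ADP data will be entered into the database by the study coordinators". The documents do not establish that one person both oversees the nutrition orders and recruits.

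**The concern.** There are two separate problems.

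**The analyst.** The coordinator and the dietician need to know the arm to deliver the intervention. The documents give no such reason for the analyst. Corrections, transformations and the missing-at-random judgement made with the arm known could shift the secondary results. Section 16.0 (15.2) intends the effect-size estimates from this pilot to set the sample size of a larger trial, and a reader could not rule out that they were influenced.

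**The sequence.** Blocking balances the arms but does not conceal the sequence. Because each block must end in balance, earlier assignments carry information about later ones. Someone who knows the next arm could be influenced in whom to approach or consent after birth, or in applying the exclusion for infants likely to be transferred (Section 9.2), which rests on judgement. Families who consent before delivery do so before their place in the sequence is known, so not every predictable allocation is exposed. Their share is not given.

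**Working it through.** **The plan's own figures.** Section 16.0 (15.2) allows for about 12% loss: 35 / (1 - 0.12) = 39.8, so 40 per group and 80 in total, as stated. The weekly energy totals in the Section 4.1 table give 431/7 = 61.6 and 547.5/7 = 78.2 kcal/kg/day, as printed. This planned gap is why intake data can reveal the arm.

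**Inputs for predictability.** From Section 4.1 and Section 16.0: 80 infants, equal arms, three strata. Assumed, because not stated: about 27 infants per stratum (80/3), a fixed block length known to the guesser, and a guesser who knows all past assignments in the stratum.

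**Complete blocks.** For length 2h:

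- Share of allocations certain in advance = 1/(h+1).
- Expected correct guesses per block, always guessing the arm used less so far = h + (4^h / C(2h,h) - 1)/2.

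Length 2: 1/2 certain; 1 + (4/2 - 1)/2 = 1.5 of 2 correct (75.0%).
Length 4: 1/3 certain; 2 + (16/6 - 1)/2 = 2.83 of 4 correct (70.8%).
Length 6: 1/4 certain; 3 + (64/20 - 1)/2 = 4.1 of 6 correct (68.3%).

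**Cut at 27 infants.** The last block is incomplete, which lowers both figures slightly.

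| Length | Certain | Share | Of 80 | Correct guesses |
|---|---|---|---|---|
| 2 | 13 × 1 + 0 = 13 | 48.1% | 38.5 | 20.0/27 = 74.1% |
| 4 | 6 × 4/3 + 1/3 = 8.33 | 30.9% | 24.7 | 18.83/27 = 69.8% |
| 6 | 4 × 1.5 + 0 = 6 | 22.2% | 17.8 | 18.1/27 = 67.0% |

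**Unequal strata.** Certain allocations of 80, for lengths 2, 4 and 6:

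- 27/27/26: 39.0, 24.7, 18.0
- 15/35/30: 39.0, 24.7, 18.5
- 10/20/50: 40.0, 25.3, 18.1

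The assumption about stratum sizes matters little.

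**Randomly varied lengths.** Here the guesser knows the set of lengths but not the length of any one block, and makes the best Bayesian guess (8,000 simulated sequences of 27).

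| Lengths | Certain | Of 80 | Correct guesses |
|---|---|---|---|
| 2/4 | 10.5% | 8.4 | 71.3% |
| 4/6 | 5.7% | 4.6 | 68.4% |
| 2/4/6 | 3.8% | 3.0 | 69.3% |
| 4/6/8 | 2.3% | 1.8 | 67.1% |

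True unpredictability would be 0% certain and 50% correct. Varying the lengths removes most certain predictions but does not bring guessing back to chance.

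**The analyst.** No arithmetic applies. Section 5.1 unblinds the analyst without a time limit, and Section 16.0 gives the same role open choices. Nothing requires those choices to be settled before the arm is known.

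**The case against.** **On the analyst.** Much is already fixed. Body composition is converted to z scores on reference data and the VEP outcome is P100 latency (Section 5.2). The main models and intention-to-treat are named, and results with and without imputation are compared (Section 16.0). ERP artefacts are removed by someone else, and the data manager checks values against source (15.3). The plan provides for no outlier exclusion. Silence about timing does not show that cleaning is done with arms known, and distributional checks can be made on pooled data. Coding the arms cannot protect the primary outcome, because first-week intake reveals the arm. All of this stands and narrows the point. It does not settle the transformation and correction choices before the arm is known.

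**On the sequence.** The percentages for fixed blocks describe an assumed scheme. Varied blocks may already be in use, and leaving block lengths out of a protocol is good practice. The risk depends on an unblinded person also recruiting, which is plausible from the shared title but unproven. Consent before delivery where possible, randomisation after consent and admission, and expected participation above 70% (Section 24.1) limit how far foreknowledge could be used. These limits stand, but the sentence in Section 4.1 is wrong for any block length.

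**On the remedy.** Varied lengths alone are a weak fix. Mixes of 2/4, 4/6 or 2/4/6 are easier to guess (71.3%, 68.4%, 69.3%) than a fixed 6 (67.0%), although far fewer allocations are certain. This stands, so concealed custody of the sequence matters more than the choice of lengths.

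**Conclusion.** Both parts hold.

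The claim that permuted blocks prevent prediction is incorrect as written for anyone who knows past assignments, and Section 5.1 leaves such people in the trial. With a known fixed length of 2 to 6, about 18 to 39 of 80 allocations would be certain. With varied, undisclosed lengths, about 2 to 8 would be. In either case roughly two thirds to three quarters of guesses would be correct. These sizes rest on the assumed block lengths, about 27 infants per stratum and full knowledge of the stratum's history. They measure predictability, not bias in the results.

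The open-ended unblinding of the analyst is a narrower weakness. It concerns the secondary outcomes, mainly through transformations, the analyst's own corrections and the missing-at-random judgement. Its effect cannot be quantified from the documents.

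Confidence is medium: the wording is clear, but actual practice on block lengths, envelopes and staffing is not described.

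**What to change.** **Section 5.1 (with Section 16.0).** Have the analyst work with arms coded A and B until cleaning, transformation and imputation decisions for the secondary outcomes are documented and locked. Keep first-week intake in a separate file until then. Because intake is the primary outcome and cannot be masked this way, write its outlier and correction rules before any data are seen.

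**Section 4.1.** Replace the sentence on unpredictability with the following provisions:

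- Allocate in sequence from a concealed list, or from sequentially numbered, opaque, sealed envelopes, held by existing staff outside enrolment.
- Record eligibility before the envelope is opened, in addition to the consent and admission already required.
- Use randomly varied, undisclosed block lengths within each stratum. Keep the lengths in a restricted document, since Section 24.1 gives care staff copies of the protocol.
- State that this removes most certain predictions but not above-chance guessing.

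**Cost.** Protocol wording, one allocation list with varied blocks, and slightly more data handling for the separate intake file. No extra infants, visits or measurements.

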### 6.0 Data and Specimen Banking

- 6.1 Storage and Access: Data from the various domains will be entered by the study personnel into a web-based secure database (RedCap) for storage, retrieval and analysis. This database will be password protected and only accessible to study personnel. The datasets will then be securely stored using Box.com per HRPP policy. We will need to download them to our University/AHC desktops for statistical analysis, however only a subset of the team will be given access to all files (study coordinator and PI) and the rest will have access to the deidentified files only. This data will be kept indefinitely to allow for the possibility of adding future study visits and/or future analyses. There will be no specimen banking.
- 6.2 Data: The full dataset for the study will be maintained as above, including demographic information, pregnancy history and ultrasound results, details of delivery, clinical history of infant including nutritional intake, blood test results, growth measurements and neurodevelopmental testing results.
- 6.3 Release/Sharing: Sharing of this data outside of our study personnel will only occur after appropriate IRB approval of additional studies or analyses. When possible, the data shared will be de-identified.

### 7.0 Sharing of Results with Participants

7.1 Results of routine laboratory tests will be shared with families in the usual manner per clinical routine. Weekly measurement results including body composition measurements will also be shared with families via a weekly measurement card for their records. ERP/VEP results will be shared with families who wish to receive them.

Families will be asked on the consent form if they wish to receive the study results when they are published. If they desire to receive the results, they will be emailed or mailed to the family per their preference when they are available.

#### 8.0 Study Duration

8.1 Each individual participant in the study will be enrolled throughout their hospitalization and then out through their 4 month corrected age visit. For most patients, this will be a total of approximately 6-8 months. It is expected to take approximately 18 months to enroll all of the patients in this study. It is expected to take approximately 2 years to complete enrollment and all study visits. It will likely take an additional 6 months to complete data analysis.

#### 9.0 Study Population

- 9.1 Inclusion Criteria: We will include VLBW (birth weight <1500grams) preterm (gestational age (GA) at birth < 32 weeks) infants admitted to the University of Minnesota Masonic Children's Hospital NICU, for which written informed consent can be secured from a parent within 12 hours of birth.
- 9.2 Exclusion Criteria: Infants who are diagnosed prenatally with a clinical condition (other than prematurity) that is known to affect growth rate, adiposity, or neurocognitive development, who experienced severe birth asphyxia, who are enrolled in another study affecting nutritional management, or who are likely to be transferred out of the NICU will be excluded from participation.
- 9.3 Screening: Admissions to the antepartum unit and to the NICU will be screened daily by the inpatient research coordinator for potential eligibility for the trial.

